#### **8.4 Safety signal detection**

Selected data from this study will be reviewed periodically to detect as early as possible any safety concern(s) related to the study medication so that Investigators, clinical study participants, regulatory authorities, and IRBs/IECs will be informed appropriately and as early as possible.

The study physician or medically qualified designee/equivalent will conduct an ongoing review of SAEs and perform ongoing SAE reconciliations in collaboration with the Patient Safety representative.

As appropriate for the stage of development and accumulated experience with the study medication, medically qualified personnel at UCB may identify additional safety measures (eg, AEs, vital signs, laboratory or ECG results) for which data will be periodically reviewed during the course of the study.

#### **8.5 Treatment of overdose**

For this study, any administration of UCB0599 totaling greater than 360mg within approximately a 24-hour time period will be considered an overdose.

Overdose events are only considered AEs or SAEs if there are associated clinical signs and symptoms or if the act of taking the excess study medication itself is an AE or SAE (eg, suicide attempt).

UCB does not recommend specific treatment for an overdose.

In the event of an overdose, the Investigator or treating physician should:

- Stop dosing and contact the Medical Monitor immediately.
- Closely monitor the participant for any AE/SAE and laboratory abnormalities until UCB0599 can no longer be detected systemically (approximately 5 days).
- Document the quantity of the excess dose as well as the duration of the overdose in the eCRF.

Decisions regarding dose interruptions or modifications will be made by the Investigator in consultation with the Medical Monitor based on the clinical evaluation of the participant.

#### **8.6 Pharmacokinetics**

Pharmacokinetic sampling will be mandatory for study participation in Part A and Part B. Samples will be collected predose and at several time points after study medication administration. These samples are a required component of the protocol as specified in the Schedule of Activities (Section 1.3 for Part A [Table 1-3] and Part B [Table 1-4]).

Any changes in the timing or addition of time points for any planned study assessments must be documented and approved by the relevant study team member and then archived in the Sponsor and site study files, but will not constitute a protocol amendment. The IEC will be informed of any safety issues that require alteration of the safety monitoring scheme or amendment of the ICF.

Additional samples may be collected at additional time points during the study if warranted and agreed upon between the Investigator and the Sponsor. Instructions for the collection and handling of biological samples will be provided by the Sponsor. The actual date and time (24 hour clock time) of each sample will be recorded.

See Section 5.3 for guidelines on lifestyle restrictions including details on meals and dietary restrictions.

#### **8.6.1           Part A**

Plasma samples (approximately 2mL whole blood collection) will be used to evaluate the primary PK parameters (Table 3-1), in which the relative bioavailability of 2 new UCB0599 formulations will be assessed compared with a reference ‘granules in capsule’ formulation in the presence and absence of esomeprazole in healthy participants. Estimated PK parameters may be used for the exposure-response assessment of safety and tolerability observations of each formulation and across formulations in the absence/presence of esomeprazole (Table 3-1).

Collection of samples for other PK parameters will be done as part of the study objectives and will evaluate the PK of UCB0599 for each tested formulation in the presence and absence of esomeprazole; and the PK of UCB0599 and its metabolites CCI [REDACTED] after a single dose of UCB0599 alone and co-administrated with esomeprazole (Table 3-1). Instructions pertaining to sample collection, processing, storage, labeling, and shipping are provided in the laboratory manual for this study. All collected samples may be used for research purposes focusing on method development and assay development. Collection of these samples will enable evaluation of relevant pharmacological information to support UCB0599 new formulation development.

#### **8.6.2           Use of residual plasma samples (Part A only)**

Any residual and/or surplus PK plasma samples remaining after the protocol-defined interim analysis has been performed may be used for additional exploratory analysis related to the purpose of this study. This may include, but is not limited to, biomarker assay development/optimization, protein binding, exploratory metabolite profiling/quantification, or other bioanalytical purposes (eg, cross check between different sites and/or stability assessment). Given the exploratory nature of the work, the analytical method used for those assessments will not be validated. As such, the results from this exploratory analysis will not be included in the Clinical Study Report.

Residual and/or surplus PK plasma samples will not be used for any genetic biomarker research.

#### **8.6.3           Part B**

Plasma samples (approximately 2mL whole blood collection) will be collected to evaluate the plasma concentrations of UCB0599, as well as to further assess other PK endpoints of UCB0599 and its metabolites CCI [REDACTED], as specified in the Schedule of Activities (Section 1.3), after administration of a single oral dose of the formulation selected from Part A in

healthy participants of Japanese and Chinese origins. See Section 3 (Table 3-2) for details on primary and other PK endpoints.

Estimated PK parameters may be used for the exposure-response assessment of safety and tolerability observations.

Drug concentration information that would unblind the study will not be reported to investigative sites or blinded personnel until the study has been unblinded.

## **8.7 Biomarkers**

Genetic blood sampling will be mandatory for study participation. Collection of deoxyribonucleic acid (DNA) blood samples will occur as specified in the Schedule of Activities (Section 1.3) and may be used for exploratory research to further the understanding of how genetic variation may influence the metabolism, distribution, and elimination of UCB0599. No other analysis will be performed on the participant's DNA. Instructions pertaining to sample collection, processing, storage, labeling, and shipping are provided in the laboratory manual for this study.

Additional information is presented in Appendix 5 (Section 10.5).

## **8.8 Medical resource utilization and health economics**

Not applicable.

## **9 STATISTICAL CONSIDERATIONS**

A description of statistical methods follows and will be described in more detail in the Statistical Analysis Plan (SAP).

### **9.1 Definition of analysis sets**

The following analysis sets will be used:

- All Study Participants (ASP): All study participants who signed the ICF for Part A or Part B, separately.
- The Randomized Sets A (RS A) and B (RS B): All study participants who are randomized to Part A or to Part B, respectively. Of note, this set will only be produced if it differs from the Safety Set (SS).
- The Safety Sets (SS; referred to as SS A and SS B for Part A and Part B, respectively): All study participants who are randomized and receive full or partial study medication according to the treatment that the participants actually received. The SS will be used for summaries of demographics, medical history, prior and concomitant medications, study medication exposure, and general safety outcomes such as AEs, laboratory parameters, vital signs, and ECGs.
- The Pharmacokinetic Set (PKS; referred to as PKS A and PKS B for Part A and Part B, respectively): This is a subset of the SS and consists of those study participants who received at least 1 total dose of study medication and have at least 1 observable PK measurement without important protocol deviations that would affect the PK.

## **9.2 General statistical considerations**

All analyses will be performed using SAS® version 9.4 or later (SAS Institute, Cary, NC, US).

The appropriate noncompartmental PK parameters will be calculated from the UCB0599 plasma concentration-time data using Phoenix® WinNonlin® Version 8.0 or higher. Actual sample times will be used in the calculations of the PK parameters.

For calculation of the plasma PK parameters of UCB0599 and metabolites, the actual sampling time points will be used in order to evaluate the PK parameters.

## **9.3 Planned efficacy outcome analyses**

There will be no efficacy endpoint in this study.

## **9.4 Planned PK outcome analyses**

### **9.4.1 PK parameters to be measured**

The following PK parameters will be determined using the actual recorded sampling times and non-compartmental method(s) with Phoenix WinNonlin® (Version 8.3.4), as applicable:  $C_{max}$ ,  $t_{max}$ ,  $AUC_{last}$ ,  $AUC_{inf}$ ,  $AUC\%Extrap$ ,  $t_{1/2}$ ,  $\text{Lambda}_z (\lambda_z)$ ,  $CL/F$  (UCB0599 only),  $Vz/F$  (UCB0599),  $MRC_{max}$ , and  $MRAUC_{inf}$  from the plasma concentration-time data.

This document cannot be used to support any marketing application and any extensions or variations thereof.  
PUBLIC COPY

**Table 9-1: Non-compartmental PK parameters for UCB0599 in plasma**

PK Parameter	Definition
AUC inf	The AUC from time zero to infinity (mass * time * volume  ).
AUC last	The AUC from time zero to the last measurable drug concentration sampling time (t last ) (mass * time * volume  ).
C max	The maximum (peak) observed drug concentration following a single dose administration (mass * volume  ).
t max	The time to reach maximum (peak) drug concentration following a single dose administration (time).
t 1/2	The elimination half-life associated with the terminal slope ( $\lambda_z$ ) of a semilogarithmic concentration-time curve (time).
CL/F a	The total apparent body clearance of drug (volume/time).
Vz/F a	The apparent volume of distribution during terminal phase (associated with $\lambda_z$ ) (volume).
Lambda_z ( $\lambda_z$ )	Terminal elimination rate constant (1/time).
AUC%Extrap b	Area under the <matrix> concentration-time curve extrapolated from the time t to infinity as a percentage of total AUC.
Rsq_adj c	Square of the correlation coefficient (adjusted for the number of data points included) associated with $\lambda_z$ .
MRC max d	C max metabolite to parent ratio.
MRAUC inf d	AUC 0-inf metabolite to parent ratio.

a For UCB0599 onlyb AUC%Extrap is listed if AUCinf is presentedc Rsq\_adj is listed onlyd Metabolites only

The linear trapezoidal rule will be used for AUC calculation. Regression analysis of the terminal plasma elimination phase for the determination of t1/2 will include at least 3 data points after Cmax. If the Rsq\_adj value of the regression analysis of the terminal phase is less than 0.75, no value is to be reported for AUCinf, t1/2, CL/F, and Vz/F.

#### **9.4.2 Analysis of the primary PK endpoint**

##### **9.4.2.1 Part A**

The plasma concentration-time profiles and PK parameters of UCB0599 will be summarized by dose level and group using descriptive statistics (number of available observations, arithmetic mean, standard deviation, geometric mean, coefficient of variation of geometric mean, median, minimum, and maximum). Values below the lower limit of quantification (LLOQ) will be reported with a clear sign indicating that they were below the LLOQ. Descriptive statistics of concentrations will be calculated if at least two-thirds of the individual data points are quantifiable ( $\geq$ LLOQ).

The primary objective of Part A is to estimate the relative bioavailability of 2 new UCB0599 formulations (film-coated tablet containing CCI with or without encapsulation) versus the current reference formulation (granules in capsule) under normal or elevated pH gastric conditions in healthy participants. The Part A primary PK endpoints are  $C_{max}$ ,  $AUC_{0-t}$ , and  $AUC_{inf}$  for UCB0599 administered without and with esomeprazole. Descriptive statistics will be executed for all PK parameters estimated.

Individual concentration-time profiles will be displayed graphically on a linear-linear scale and semilogarithmic scale. Overall geometric mean plasma concentrations-time curves and corresponding 95% CIs will be displayed by formulation and condition (elevated and normal gastric pH).

The PK parameters ( $C_{max}$ ,  $AUC_{0-t}$ , and  $AUC_{inf}$ ) will be used to estimate the following:

- Primary objective: the relative bioavailability of 2 new UCB0599 formulations versus reference 'granules in capsule' formulation under elevated gastric pH and under normal conditions

The primary comparisons of interest are:

- non-encapsulated tablets vs granules in capsule under normal pH condition
- encapsulated tablets vs granules in capsule under normal pH condition
- non-encapsulated tablets vs granules in capsule under elevated pH condition
- encapsulated tablets vs granules in capsule under elevated pH condition

In order to estimate these comparisons, the primary analysis model will be applied to the 2 sets of data separately; namely, the data under normal gastric pH condition (first 3-period crossover design substudy) and the data under elevated gastric pH condition (second 3-period crossover design substudy).

Following log-transformation, the primary PK parameters ( $C_{max}$ ,  $AUC_{0-t}$ , and  $AUC_{inf}$ ) will each be evaluated according to a linear mixed effect model with a random intercept term for participant and fixed effect categorical terms for treatment, sequence, and period to account for the crossover nature of the design for Part A.

The PK analyses will be performed on the PK data from Part A.

For each set of data, the estimate of the ratio of geometric mean for the UCB0599 film-coated tablet versus capsule (reference formulation) and for the UCB0599 encapsulated tablet versus capsule (reference formulation) treatments will be calculated along with its corresponding 90% confidence interval (CI) in order to assess the UCB0599 relative bioavailability.

Sensitivity analyses to the model above may be performed on the PK parameters, such as linear mixed effect models applied separately to the data for each new formulation versus reference formulation.

Another objective of the study is to estimate the relative bioavailability of UCB0599 under elevated gastric pH versus normal gastric pH for each tested formulation. To that effect, a supplementary analysis will be performed using the PK parameters ( $C_{max}$ ,  $AUC_{0-t}$ , and  $AUC_{inf}$ ) where data from all 6 periods (normal and elevated gastric pH data) will be combined into a

single linear mixed effect model with a random intercept for participant and fixed effect categorical terms for treatment, gastric status, treatment by gastric status interaction, sequence, and period within substudy (ie, 3-level categorical variable). As before, ratios and corresponding 90% CIs will be obtained for the UCB0599 capsule, non-encapsulated tablet, or encapsulated tablet under elevated gastric pH condition versus the respective formulation under normal gastric pH condition.

#### **9.4.2.2 Part B**

The primary objective of Part B is to evaluate the plasma PK of UCB0599 after administration of a single dose of an oral formulation in healthy participants of Japanese and Chinese origins.

The PK parameters ( $C_{max}$ ,  $AUC_{0-t}$ , and  $AUC_{inf}$ ) will be used to estimate the following:

- PK parameters for the 3 groups (Part A healthy participants, Japanese participants, and Chinese participants)
- Dose proportionality for each group, including graphical presentation

Individual concentration-time profiles will be displayed graphically on a linear-linear scale and semilogarithmic scale.

Overall geometric mean plasma concentration-time curves and corresponding 95% CIs will be displayed by group.

No formal comparison will be made.

The PK analyses will be performed on the PK data from Part B.

The plasma concentration-time profiles and PK parameters of UCB0599 will be summarized by dose level and group using descriptive statistics (number of available observations, arithmetic mean, standard deviation, geometric mean, coefficient of variation of geometric mean, median, minimum, and maximum). Values below the LLOQ will be reported with a clear sign indicating that they were below the LLOQ. Descriptive statistics of concentrations will be calculated if at least two-thirds of the individual data points are quantifiable ( $\geq LLOQ$ ).

Descriptive statistics will be executed for all PK parameters estimated by ethnicity and dose. For  $t_{max}$ , only the median, minimum, and maximum will be reported.

The PK descriptive statistics from Part A healthy participants who receive 180mg dose of the formulation used in Part B will be presented alongside.

Dose proportionality for  $C_{max}$ ,  $AUC_{0-t}$ , and  $AUC_{inf}$  will be examined for each ethnic group and for Part A healthy participants who receive a 180mg dose of the formulation used in Part B and graphically reported. Dose proportionality could be achieved by dose normalization and log-transforming  $C_{max}$  and AUC data, in which a linear regression  $C_{max}$  versus dose and AUC versus dose will be used to assess if the slope of the regression line deviates statistically significantly from zero. If the slope is not different from zero, then it can be concluded that the PK is proportional to dose.

The co-primary PK endpoint data obtained for the UCB0599 formulation used in Part B at the 180mg dose under normal gastric pH condition for the three ethnicities (ie, N=36 participants from Part A, N=8 participants of Japanese origin, and N=8 participants of Chinese origin) will be log-transformed. As an exploratory analysis, transformed data will be combined into an Analysis

of Variance (ANOVA) model with fixed effect terms for cohort, assuming the data for each ethnicity come from a single parallel arm design. Point estimates for the geometric mean ratios and corresponding 90% CIs will be obtained and compared between the Japanese participants versus the Part A participants, and between the Chinese participants versus the Part A participants using least squares means and root mean squares of error from the model with subsequent exponential transformation.

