### **Treatment groups and duration**

Part A consists of the following (for a total duration of up to 68 days):

- A 28-day Screening Period (2 to 28 days before administration of study medication)
- A Baseline health status on admission to study site on Day -1.
- 6 treatment periods (each treatment period is followed by a 4-day Washout Period)
  - The first 3 periods include the evaluation of UCB0599 PK following its single-dose administration (180mg) of each formulation under normal gastric pH conditions.
  - The second 3 periods include the evaluation of UCB0599 PK following its single-dose administration (180mg) of each formulation under the condition of elevated gastric pH. The elevated gastric pH will be achieved by co-administering esomeprazole 40mg once daily (QD) over the duration of the 3 treatment periods (Day 14 to Day 33; [Table 1-1](#)).
- A 7-day Safety Follow-Up (SFU) Period

In Treatment Period 1 through Period 3 for Part A, study participants will fast overnight for at least 10 hours prior to study medication administration on Day 1, Day 6, and Day 11, according to the randomization scheme (see [Table 1-1](#)), and will continue to fast for at least 4 hours post-study medication administration; thereafter participants will be given a standard breakfast or light snack. In Treatment Period 4 through Period 6, study participants will fast overnight for at least 9 hours prior to esomeprazole administration on Day 19, Day 24, and Day 29, and will continue to fast prior to study medication administration (1 hour following esomeprazole administration) and for at least 4 hours post-study medication administration (see [Table 1-1](#)); thereafter, participants will be given a standard meal (ie, lunch). In between each Treatment Period, participants will undergo a 4-day Washout Period. On other days during the Treatment Period, study participants will receive standard meals and snacks at appropriate times as indicated by the clinic center (see [Table 1-3](#)). During the whole treatment, participants will remain under close medical supervision in the clinic.

On Day 33, after all the scheduled procedures have been performed, the participant may leave the clinic provided that, in the opinion of the Investigator, there are no safety concerns. Study

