#### **4.3 Justification for dose**

In Part A, the UCB0599 dose level of 180mg single dose is being selected based on the PK properties of UCB0599. Upon oral intake of doses 90mg to 450mg, both  $C_{max}$  and AUC increase approximately linearly with dose, indicating dose proportionality. In addition, clinical data show that AUC at steady state over the dose interval is similar to  $AUC_{inf}$  after single dose, suggesting linear behavior of UCB0599 in the clinically tested dose range of 180mg/day to 360mg/day; hence UCB0599 180mg single dose administration is projected to provide exposure information that can be used to bridge between the current clinical formulation and a new formulation.

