5.1.1.4 Definition of Analysis by Variables

Table 5-3: Definition of Analysis by Variables for Part A

Term	Variables
Sequence	Sequence 1 (ABC)
	Sequence 2 (ACB)
	Sequence 3 (BCA)
	Sequence 4 (BAC)
	Sequence 5 (CAB)
	Sequence 6 (CBA)
Formulation	180mg (90mg x 2 granules in capsule)
	180mg non-encapsulated tablet containing PPD
	180mg encapsulated tablet containing PPD
Gastric condition	Normal gastric pH
	Elevated gastric pH

Note: A: 180mg (90mg x 2 granules in capsule) current clinical formulation (reference formulation); B: 180mg non-encapsulated tablet containing PPD ; C: 180mg encapsulated tablet containing PPD .

Table 5-4: Definition of Analysis by Variables for Part B

Term	Variables
Sequence	Sequence 1 (C=1, J=1; 90mg → 180mg)
	Sequence 2 (C=4, J=4; 90mg → 180mg)

Table 5-4: Definition of Analysis by Variables for Part B

Term	Variables
	Sequence 3 (C=1, J=1; 180mg → 360mg)
	Sequence 4 (C=4, J=4; 180mg → 360mg)
	Sequence 5 (C=1, J=1; 360mg → 90mg)
	Sequence 6 (C=4, J=4; 360mg → 90mg)
Dose level	Pooled Placebo
	90mg
	180mg
	360mg
Participant group	Japanese participants
	Chinese participants
	Part A healthy participants under normal gastric pH condition on the formulation chosen for Part B

C=Chinese participants; J=Japanese participants.

Table 5-5: Analysis Performed by “by Variables”

Analysis	Part A by Variable	Part B by Variable
Disposition	Sequence	Sequence
Medical History		
Concomitant Medications		
Important Protocol Deviations		
PK Concentration	Formulation and gastric condition	Dose level and participant group
Adverse Events	Formulation	Dose level and participant group
Laboratory Values	Time Point and Sequence	Time Point Sequence
Vital Signs		
ECG		

ECG= electrocardiogram; PK=pharmacokinetic.

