5.4.3 Part B

5.4.3.1 Analyses required for Primary Objective (on Primary PK endpoints)

Dose proportionality for C_{max} , AUC_{0-t} , and AUC_{inf} will be examined for each participant group (Table 5-3) via the power model

$$Y = \alpha + dose^{\beta}, \quad (3)$$

where α is the subject random intercept, Y is the parameter of interest, and β is the slope. The PK parameters and the dose will be logarithmically transformed prior to analysis. The power model will be estimated by regressing the log-transformed PK parameter onto the log-transformed dose.

$$\ln(Y) = \alpha + \beta * \ln(dose) \quad (4)$$

The power model will be fitted by restricted maximum likelihood (REML) using the PROC MIXED procedure in SAS, with a fixed effect term for dose level and a random effect for participant. A lack of fit test will be performed to check the linearity assumptions for appropriateness of the power model. An unstructured covariance matrix will be specified for the participant random effect. If the model fails to converge, other covariance matrices such as VC and CS may be considered.

The results of the power model will be reported after back-transformation, including the estimated dose proportionality parameter β along with corresponding 90% CI (slope ≈ 1 implies dose proportionality).

Graphical displays including observed values, regression line of the fitted values with the 90% CI will be provided for each log-transformed PK parameter vs. log-transformed dose.

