5.4.3.2 Exploratory analysis for Primary Objective (on Primary PK endpoints)

The co-primary PK endpoint data obtained for the groups will be log-transformed. For each dose level, the transformed data will be combined into an ANOVA model with fixed effect terms for participant group. The model may be adjusted for age, height and weight. Therefore, the impact of the Baseline (Day-1) characteristics of age, height and weight will be included in the statistical

model as fixed effect and tested by 10% significant level individually. If a fixed term has a significant effect to the model for all three primary PK parameters at 10% significant level, the term will be included to the ANOVA model as fixed effect. The SAS PROC MIXED procedure will be used. Point estimates for the geometric mean ratios and corresponding 90% CIs will be obtained and compared between the Japanese participants versus the Part A participants (healthy participants on normal gastric condition on the formulation chosen for Part B), and between the Chinese participants versus the Part A using least squares means and root mean squares of error from the model with subsequent exponential transformation.

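### Dose proportionality is planned for Part A, which has one dose; the SAP drops the 180 mg limit on ratios to Part A; and the protocol treats a non-significant slope as proof of proportionality

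*Protocol*

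**What the plan says.** **Part A dose.** Periods 1 to 3 evaluate PK "following its single-dose administration (180mg) of each formulation under normal gastric pH conditions" (Protocol, Treatment groups and duration). Periods 4 to 6 use the same dose with esomeprazole. Protocol 4.3 confirms it: "In Part A, the UCB0599 dose level of 180mg single dose is being selected based on the PK properties of UCB0599".

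**Dose proportionality, protocol.** Section 9.4.2.2 names three groups (Part A, Japanese, Chinese), lists dose proportionality for each, and then says that it "will be examined for each ethnic group and for Part A healthy participants who receive a 180mg dose" of the Part B formulation. It offers, in permissive terms, a regression of dose-normalised, log-transformed data on dose. It then states without qualification that proportionality can be concluded when the slope does not differ from zero.

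**Dose proportionality, SAP.** In Section 5.4.3.1 it "will be examined for each participant group (Table 5-3) via the power model". Participant groups are in fact defined in Table 5-4, where the third is "Part A healthy participants under normal gastric pH condition on the formulation chosen for Part B". The model has a participant random effect and a lack-of-fit test. It reports beta with a 90% CI and says that a slope of about 1 implies proportionality. No limits are given.

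**Ratios to Part A.** Protocol 9.4.2.2 takes the data "at the 180mg dose under normal gastric pH condition for the three ethnicities", with N=36, 8 and 8. SAP 5.4.3.2 says instead: "For each dose level, the transformed data will be combined into an ANOVA model with fixed effect terms for participant group". Estimates are then "compared between the Japanese participants versus the Part A participants (healthy participants on normal gastric condition", and likewise for Chinese versus Part A. No other ratio is named.

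**Record of changes.** SAP 6.4 says that there is nothing to report. The SAP (version 1, 05 Sep 2023) rests on the protocol of 02 Mar 2023.

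**The concern.** Two of the planned analyses ask for quantities that the design cannot supply: a dose slope in a group with one dose, and ratios to Part A at two doses that Part A never received. Separately, the protocol turns failure to reject into a positive conclusion. In a small group that conclusion is the likely outcome even when exposure departs materially from proportionality.

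The SAP uses a different method, but its own interpretive statement has no limits either, and the change is not listed. The report would therefore have two unreconciled rules to draw on. Dose proportionality belongs to the Part B primary PK analysis, and Protocol 4.3 says that the three doses were set in a common ratio of 2 partly to evaluate it.

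**Working it through.** **Inputs from the documents**
- Part B active sequences, 4 participants each per ethnic group: 90 then 180, 180 then 360, 360 then 90 mg (Protocol 4.1.2).
- Within-participant variance of ln(Cmax): 0.0782 (Protocol 9.9.1). No AUC variance is given.
- Part A: 36 completers, all at 180 mg.

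**Assumptions (not in the documents)**
- Between-participant variance s²b of 0.04, 0.09 or 0.16.
- Two-sided 5% level for the protocol test.
- Illustrative departure: dose-normalised exposure changes by 25% over the 4-fold range, so beta − 1 = ln(1.25)/ln(4) = 0.161.

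**1. The plan's own figures.** √(exp(0.0782) − 1) = 0.285, the stated 28.5%. Each dose occurs in two active sequences of 4, giving the stated 8 participants per dose. The Part A figure of 36 also reproduces: two one-sided tests with SE = √(2 × 0.0782/36) and 68 df give 91.2% power, against the 90% sought.

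**2. Part A slope.** With every row equal to (1, ln 180), the design matrix has rank 1 for 2 parameters. Neither the protocol regression nor the SAP power model can return a slope. For each Part B ethnic group the rank is 2.

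**3. Ratios to Part A by dose**

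| Dose | Part A | Japanese | Chinese | Ratio to Part A |
|---|---|---|---|---|
| 90 mg | 0 | 8 | 8 | not estimable |
| 180 mg | 36 | 8 | 8 | estimable |
| 360 mg | 0 | 8 | 8 | not estimable |

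Expected precision is t × √[(s²b + 0.0782)(1/n1 + 1/n2)] at 90% confidence.
- 36 versus 8 (49 df): half-widths 0.225, 0.269, 0.320 on the log scale, a factor of 1.25 to 1.38 either side.
- 8 versus 8 (14 df), Japanese versus Chinese: 0.303, 0.361, 0.430, a factor of 1.35 to 1.54.

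**4. Information on the slope in one ethnic group.** Work in units of (ln 2)² = 0.4805.
- Within-participant sum of squares: 4 × ½ + 4 × ½ + 4 × 2 = 12, so W = 5.765.
- Between-participant: 2 × (4 × 0.25 + 4 × 0.25) = 4, so B = 1.922.
- Total T = 7.687.

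**5. Protocol rule (plain regression).** The slope's true SE is √[W × 0.0782 + B × (0.0782 + 2s²b)]/T, which is 0.113 at s²b = 0.04 and 0.143 at 0.16. The SE that plain regression reports is roughly √[(0.0782 + s²b)/T], or 0.124 and 0.176. It is too large because the pairing of doses within participants is ignored. Simulation (40,000 trials per setting) gives:

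| s²b | Non-significant at 25% departure, on ln(dose) | Same, on dose | Rejected at true proportionality, on ln(dose) |
|---|---|---|---|
| 0.04 | 0.774 | 0.786 | 0.034 |
| 0.09 | 0.845 | 0.855 | 0.024 |
| 0.16 | 0.898 | 0.901 | 0.017 |

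**6. SAP power model, random intercept.** SE of beta = 1/√[W/0.0782 + B/(0.0782 + 2s²b)] = 0.108, 0.111, 0.113. The 90% CI half-width on 11 df is 0.194, 0.199, 0.203. At an estimate of exactly 1, the interval therefore runs from about 0.80 to 1.20, and 4^0.20 = 1.32. Data centred on proportionality would still be compatible with a change of about a third in dose-normalised Cmax over the range.

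**The case against.** The best reply is that the SAP governs the analysis and has already replaced the weak rule with a sounder one. The protocol introduces its regression permissively, and Section 9 leaves detail to the SAP, so the power model can be read as elaboration. This stands in part: the SAP was free to choose a power model, and the 77% to 90% describes a rule that the SAP would not run. Much of that figure also reflects sample size. A two-sided 5% test from a random-intercept model (11 df) would miss the same departure in about 72% to 74% of trials. But the protocol's concluding sentence is not permissive, it remains in Amendment 1 (26 Oct 2023, after the SAP), and the SAP does not disown it.

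A second reply is that Part A's 180 mg points may simply be overlaid on the plot. The protocol does mention graphical reporting. However, it provides separately for showing Part A descriptive statistics alongside, and both documents name Part A among the groups for which proportionality is examined.

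Three stronger readings are tempting and are not supported:
- *The Part A comparisons would give wrong estimates.* Setting 90 and 360 mg data against un-normalised 180 mg Part A data would give ratios of 0.50 and 2.00 under exact proportionality and no ethnic difference. The SAP does not plan that. As written, those cells give no estimate.
- *The trial will probably declare proportionality falsely.* The miss rate belongs to the protocol rule and depends on the assumed variances, level and departure.
- *The SAP method would by itself prevent an unsupported conclusion.* Its statement about a slope near 1 has no limits, so it would not.

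The SAP's use of the 02 Mar 2023 protocol does not explain the differences. That version is not available here, but for Section 9.4.2.2 the amendment summary lists only formulation wording, apart from unsummarised minor edits.

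**Conclusion.** The point holds, at a severity of minor to should-fix. The Part A slope and the ratios to Part A at 90 and 360 mg cannot be estimated; this follows from the design and needs no assumption. The protocol's rule treats non-significance as proof and is unsound in groups of 12. The size of that weakness, a 77% to 90% chance of missing a 25% departure, applies to Cmax only and rests on the assumptions listed in the working. The SAP method is better but lacks limits or a caution on interpretation, and the change is unrecorded.

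The practical effect is limited. Part A formulation comparisons, sample size and cohort progression do not depend on any of this, and the ethnic ANOVA is exploratory.

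**What to change.** - **SAP 5.4.3.1:** restrict dose proportionality to the Japanese and Chinese groups and show Part A 180 mg data descriptively. Keep the power model and lack-of-fit test. Report beta on its own scale, not back-transformed, with its 90% CI as an estimate, and state that a CI including 1 does not by itself establish proportionality. Correct the table reference to Table 5-4.
- **SAP 5.4.3.2:** restrict ratios to Part A to 180 mg. At 90 and 360 mg report only the Japanese and Chinese geometric means or their ratio.
- **SAP 6.4:** record the change of method from Protocol 9.4.2.2.
- **Protocol 9.4.2.2:** at the next amendment, replace the conclusion from a slope not different from zero with the SAP approach, and remove Part A from the dose-proportionality sentences.

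No data or participants are added. The SAP revision settles most of it. The protocol change needs IRB/IEC approval (Protocol 10.1.1), so it can wait if the SAP records the change first. The one downside is that the report can no longer declare proportionality from a non-significant slope.
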